10.3 Data Analyses

10.3.1 Statistical Methods

Due to the relatively small size of the study descriptive statistics will be presented for demographics, baseline characteristics, procedure duration and product performance (effectiveness). Continuous variables will be summarized as mean, standard deviation, median, minimum and maximum. Categorical variables will be summarized as frequency and percentages.

10.3.2 Safety Analysis

For the Safety Population, the study primarily aims to rule out a 10% by-participant MACE incidence rate using the upper limit of a 2-sided 95% Wilson score confidence interval (equivalent to a 1-sided 0.025 α level) for the observed MACE incidence rate. To achieve this goal with the proposed sample size, a study incidence rate much lower than 10% needs to be observed in the study. In fact, up to 3 participants with MACE are allowed, which would be a rate of 3.5%. The Wilson score 95% confidence interval for $3/85 = 3.5\%$ is (1.2%, 9.9%). As the upper limit of 9.9% is < 10%, a 10% incidence rate can be ruled out at a 1-sided 0.025 α level.

All MACE occurrences will be descriptively reported. If there are more than three participants with MACE events, the study will be judged as not meeting its primary safety objective.

Additionally, non-MACE adverse events occurring during or after the protocol procedure will be summarized as follows. The number and proportion of participants reporting any given event will be tabulated according to the highest severity reported. Separate tables will be constructed for (a) all reported adverse events (including adverse device effects), (b) protocol procedure/device related adverse events, (c) serious adverse events, and (d) adverse events requiring study device discontinuation.

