Data Collection	
Screening
 
 a. Demographics (e.g., age, sex, race) b. Documentation of disease-related characteristics c. Previous and current treatments for disease d. Baseline (pre-procedure) cardiac enzymes 
Procedure
 
 a. Duration (1st sheath in, to the last sheath out/participant leaving cath lab) b. Device-Oriented Clinical Outcome (DOCE) c. Procedure-Oriented Clinical Outcome (POCE) d. Device deficiencies/malfunctions e. Adverse events/adverse device effects f. Procedure usability data 
Follow-up (48 hours/patient discharge & 7-10 day phone call)
 
 a. Assessment for adverse events/adverse device effects b. Cardiac enzymes at 1 hour (± 15 min) and 4-6 hours post-procedure

Sample Size	
Based on historical data regarding the event rate in the safety outcome^{2,3,4,5}, an exact binomial calculation was used to estimate sample size with the following assumptions⁶:
 
• Wilson score 95% confidence level (CL) for study MACE incidence rate, i.e. 1-sided $\alpha = (1-CL)/2 = 0.025$• True underlying MACE incidence rate = 0.02 (2% MACE rate)• Delta factor = 0.08, i.e., the goal is to reject 0.10, or a 10% MACE incidence rate, at a 1-sided p of 0.025 significance level 
A sample size of 85 evaluable participants is proposed based on the above assumptions. In order to reject a true MACE incidence rate of 10% at a 1-sided α level of 0.025, at most 3 out of 85 participants (3.5%) can have MACE in the study. The actual α level is 0.0245 if the true MACE incidence rate is 10%; the power is 0.91 if true MACE incidence rate is 2%. Assuming a 10% attrition rate, 95 participants will be enrolled.

Study Committees	Due to the relatively small size of the study, no study committees will be used but an independent medical monitor cardiologist will be used to adjudicate events and provide safety oversight for the study.

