5.0 STUDY POPULATION

5.1 General Considerations

Patients who are scheduled for percutaneous intervention to treat coronary artery disease who do not have significant comorbidities that might confound outcomes will be considered for enrollment in this trial. Due to the short follow-up and relatively inclusive selection criteria in this trial, recruitment for this trial should be straightforward.

Up to 95 participants will be enrolled in the trial in order to generate data for 85 cases in which the LiquID devices are used clinically. A participant is considered enrolled when they meet study enrollment (all inclusion and no exclusion) criteria and have signed informed consent. All enrolled participants will be assigned a study ID consisting of a 2-digit site number and a 3-digit sequential participant number (e.g., 01-005).

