10.0 STATISTICAL METHODS

10.1 Sample Size Estimation

For the primary endpoint of participant incidence of any MACE, the rates in similar prior studies²⁻⁵ provided information to establish an estimated rate for this study of 2.0%. The exact binomial probability calculation was used to determine the sample size, using the following assumptions⁶:

- 95% confidence level (CL) for study MACE incidence rate, i.e., 1-sided $\alpha = (1-CL)/2 = 0.025$
- True underlying MACE incidence rate = 0.02 (2% MACE rate)
- Sampling delta factor = 0.08, i.e., performance goal to reject = 0.10, or 10%, at a 1-sided p of 0.025 significance level

A sample size of 85 evaluable participants is proposed based on the above assumptions. In order to reject a true MACE incidence rate of 10% at a 1-sided α level of 0.025, at most 3 out of 85 participants (3.5%) can have a MACE in the study. The actual α level is 0.0245 if the true MACE incidence rate is 10% and the power is 0.91 if true MACE incidence rate is 2%

Allowing for attrition, including cases in which the study device is not used and participants that are not available for follow-up assessments, up to 95 participants may be enrolled to obtain 85 evaluable cases.

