10.2 Analysis Populations

10.2.1 Primary Endpoint (Safety) Population

The population for the primary endpoint will be any participant into whom the study device is introduced, regardless of whether or not it is used as intended.

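### If the Safety Population is smaller than 85, does section 10.3.2 leave open whether the Wilson limit or the count of 3 MACE decides the primary safety objective?

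*Combined protocol and SAP*

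**What the plan says.** Section 10.3.2 opens with the criterion for the Safety Population, in these words: "the study primarily aims to rule out a 10% by-participant MACE incidence rate using the upper limit of a 2-sided 95% Wilson score confidence interval". It applies to the observed rate, and no number of participants is attached. The next sentence turns to what this requires at the proposed sample size, and from there comes the allowance: "In fact, up to 3 participants with MACE are allowed, which would be a rate of 3.5" (percent). The section then prints the Wilson interval for 3/85, 1.2% to 9.9%, and notes that 9.9% is below 10%.

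A separate paragraph adds a failure rule with no sample size attached: "If there are more than three participants with MACE events, the study will be judged as not meeting its primary safety objective".

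The number analysed is not fixed in advance:

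- The Safety Population (10.2.1) is "any participant into whom the study device is introduced, regardless of whether or not it is used as intended".
- Enrolment is counted earlier, at consent (5.1): "A participant is considered enrolled when they meet study enrollment (all inclusion and no exclusion) criteria and have signed informed consent".
- The synopsis states "Assuming a 10% attrition rate, 95 participants will be enrolled", and 10.1 says "up to 95 participants may be enrolled to obtain 85 evaluable cases". The attrition in 10.1 covers both cases where the device is not used and participants not available for follow-up.
- Section 4.1 stops enrolment once data from 85 procedures with the device are in hand.
- Section 13.8 lets the sponsor terminate the study early.

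**The concern.** The plan expresses its one confirmatory criterion in two ways, as an interval and as a count, and they agree only over a range of sample sizes. The cap of 95 counts consented participants, while the analysis counts device introductions. The 95 is 85 inflated for average attrition, with almost no margin, so a Safety Population of 83 or fewer is possible.

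If that happened with exactly 3 MACE, the allowance sentence taken alone would suggest success, while the interval would not exclude 10%. In an open-label single-arm study, one would not want the choice between them made after the events are known. Accepting 3 events regardless of sample size would also push the exact one-sided error above the stated 0.025.

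**Working it through.** **Inputs.** Performance goal 10%, assumed true rate 2%, one-sided level 0.025, 85 evaluable participants and stated power 0.91 (10.1); at most 3 events (10.1, 10.3.2); cap of 95 and 10% attrition (synopsis, 10.1).

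**Formula.** With p = x/n and z = 1.95996, the Wilson upper limit is

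U = [p + z²/(2n) + z·√(p(1−p)/n + z²/(4n²))] / (1 + z²/n).

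**Step 1: the plan's own figures.**

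- For 3/85: U = (0.03529 + 0.02260 + 1.95996 × 0.02310)/1.04519 = 0.10316/1.04519 = 9.87%, printed as 9.9%.
- For 4/85: U = 11.48%, so 3 is the largest count that passes.
- Exact binomial: P(X ≤ 3 | 85, 0.10) = 0.0245 and P(X ≤ 3 | 85, 0.02) = 0.909.
- 85/(1 − 0.10) = 94.4, rounded up to 95.

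All of these agree with the plan.

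**Step 2: other sample sizes.** For 3/83, U = (0.03614 + 0.02314 + 1.95996 × 0.02365)/1.04628 = 0.10563/1.04628 = 10.10%. The other limits near the boundaries are:

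| Events/n | Wilson upper limit | Below 10%? |
|---|---|---|
| 3/84 | 9.98% | yes |
| 3/83 | 10.10% | no |
| 2/83 | 8.37% | yes |
| 2/69 | 9.97% | yes |
| 2/68 | 10.10% | no |
| 4/95 | 10.33% | no |
| 4/98 | 10.03% | no |
| 4/99 | 9.93% | yes |

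The criterion therefore allows 2 events for n = 69 to 83 and 3 for n = 84 to 98. Four events first pass at n = 99, above the cap, so the failure rule for more than three events is correct at every reachable size. A population somewhat above 85 changes nothing either.

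**Step 3: how often the count and the interval could part.** Suppose all 95 places are available, losses are independent with probability q, and enrolment stops at 85. Then n ≤ 83 requires at least 12 losses among 95 (12.6%), with probability P(Bin(95, 1−q) ≤ 83). At n = 83 and a true 2% rate, the chance of exactly 3 events is 0.146. Summing over the possible values of n gives:

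| Loss q | P(n ≤ 83) | P(count and interval differ), true rate 2% |
|---|---|---|
| 5% | 0.3% | 0.04% |
| 8% | 8% | 1.1% |
| 10% | 24% | 3.4% |

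At a true rate of 10% and q = 10%, always accepting 3 events gives an average one-sided error of 0.0264. Using the interval at the actual n gives 0.0211, a difference of 0.005.

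**Step 4: what the text yields at n = 83 with 3 events.** The opening criterion applies to whatever rate is observed and gives 10.10%, so 10% is not ruled out. The allowance sentence follows from a clause limited to the proposed sample size and carries the rate 3.5% = 3/85; at n = 83 the rate would be 3/83 = 3.6%, so it does not describe this case. The failure rule is silent at 3 events, since it names a condition for failure and never says that three or fewer is success. The only rule left to decide is the Wilson limit.

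**The case for a change.** The best argument for a change is that the only sentence saying how the study will be judged is a count without a sample size, and that nothing ranks it against the interval. A reader who wanted a favourable result could cite the allowance of 3, and the exact one-sided error of that reading is 0.0284 at n = 83 and 0.0353 at n = 80. A smaller population is possible: inclusion requires only that use of a guide extension is anticipated, and 10.1 itself expects some cases without the device. One clarifying sentence would cost almost nothing.

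The arithmetic stands, and so does the observation that precedence is not written down. What does not stand is the claim that the text supports both verdicts. That requires taking the allowance out of the sentence sequence that ties it to 85, and reading a failure rule as if it were also a success rule.

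The 24% chance of a short population is also an upper figure. Part of the planned 10% is for missed follow-up. Participants who miss only the 7-10 day call stay in the Safety Population, because MACE is assessed by 48 hours or discharge.

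Power does fall, from 0.91 at n = 84 to 85 to 0.77 at n = 83 under the interval criterion. That comes from having fewer participants, and no wording would restore it. Nor would printing an allowance by sample size be a clean gain: the Wilson allowance has exact one-sided error 0.0264 at n = 84 and 0.0262 at n = 69, both slightly above 0.025, so the table would need its own caveat.

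**Conclusion.** No change follows. The plan omits a statement of precedence between a rule and its own worked example, and an analyst fills that gap by computing the interval at the actual number of participants, as the opening of 10.3.2 directs. No rule as written produces a wrong verdict, and the design figures at 85 are correct.

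The case in which the wording could matter is exactly 3 MACE with 83 or fewer participants (or 2 with 68 or fewer). Its probability is about 0.04% to 3.4% at a true 2% rate. This assumes independent losses of 5% to 10% and all 95 places available. The documents give no separate rate for cases without device introduction, so that range is an assumption, with the plan's 10% as its upper end. Early termination under 13.8 could also shorten the study and is not included, because the documents give no basis for its probability. It would not change the reading: the Wilson limit at the realised number still decides.

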11.2 Summary of Potential Risks

The LiquID devices are not anticipated to add any incremental risk to interventional procedures. The following adverse events are anticipated adverse events associated with all interventional procedures:

- Access site/groin complications including but not limited to:
 - AV fistula
 - Bleeding
 - Bruising
 - Hematoma
 - Infection
 - Oozing

- Pain
 - Pseudoaneurysm
- Air embolus
- Allergic reaction to any of the following:
 - Contrast dye
 - Anesthesia anesthetic medications
 - Procedure medications
 - Materials in devices used in procedure
- Apnea
- Arrhythmias
- Arterial perforation
- Atrial septal defect
- Blood loss requiring transfusion
- Blood toxicity
- Chest pain or other symptoms due to or indicative of (but not limited to) any of the following:
 - Angina
 - Discomfort
 - Endocarditis
 - Pericardial effusion with or without cardiac tamponade
 - Pericarditis
 - Pleural effusion
- Pulmonary edema
- Dissection or thrombosis with or without vessel occlusion
- Fever
- Hypertension/hypotension
- Ischemia
- Infection
- Prolonged procedure time
- Renal insufficiency/failure
- Respiratory failure/hypoxia
- Stroke/transient ischemic attack
- Surgery to recover failed/embolized devices
- Occlusion of coronary artery branch
- Myocardial infarction
- Death
- Pain
- Procedure failure requiring additional intervention/surgery
- Toxicological response
- Vagal reaction
- Valvular damage/insufficiency
- Ventricular failure
- Vessel trauma

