12.0 ADVERSE EVENTS

12.1 Definitions

Adverse Event: Any untoward medical occurrence, unintended disease or injury, or untoward clinical signs (including abnormal laboratory findings) in participants, users or other persons, whether or not related to the device.

Adverse Device Effect: An adverse event related to the use of the device

Serious Adverse Event: An adverse event that:

- Led to death
- Led to serious deterioration in the health of the participant that resulted in:
 - A life-threatening illness or injury
 - A permanent impairment of a body function
 - In-patient or prolonged hospitalization
 - Medical or surgical intervention to prevent life-threatening illness or injury or permanent impairment to body structure or a body function
- Led to fetal distress, fetal death, or congenital abnormality or birth defect

Serious Adverse Device Effect: An adverse device effect resulting in any of the consequences characteristic of a serious adverse event.

Unanticipated Serious Adverse Device Effect: A serious adverse device effect which by its nature, incidence, severity or outcome has not been identified in the current version of the risk analysis report.

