12.3 Relatedness

The following categories of adverse events causality, both to procedure and device, are to be used (see guidance document⁹ for additional details):

Causal	Event is associated beyond reasonable doubt
Probable	Relationship seems relevant and/or cannot reasonably be explained by another cause, but additional information may be obtained
Possible	Relationship is weak but cannot be ruled out completely
Unlikely	Relationship seems not relevant and/or can be reasonably explained by another cause
Not related	Event clearly due to another cause and/or cannot reasonably be shown to be related in any manner

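### The planned adverse-event tables do not report device attribution: procedure- and device-related events share one category, and no table shows adverse device effects or serious adverse device effects alone

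*Combined protocol and SAP*

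**What the plan says.** Section 10.3.2 (Safety Analysis) summarises non-MACE adverse events by event type: "The number and proportion of participants reporting any given event will be tabulated according to the highest severity reported". It names four tables. The first takes in every event, whatever its cause. The table of related events is "b) protocol procedure/device related adverse events". The remaining two are listed as "c) serious adverse events, and (d) adverse events requiring study device discontinuation".

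Section 12.1 (Definitions) sets up separate device categories. The first is "Adverse Device Effect: An adverse event related to the use of the device". The serious form is "An adverse device effect resulting in any of the consequences characteristic of a serious adverse event", and a third category covers serious device effects that the risk analysis did not identify.

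Section 12.3 (Relatedness) provides for two attributions per event: "The following categories of adverse events causality, both to procedure and device, are to be used". The scale has five grades: causal, probable, possible, unlikely and not related.

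Other device information is planned elsewhere. Section 10.3.2 has every MACE described, and the MACE definition in section 4.2.1 includes device-caused target vessel dissection, longitudinal stent deformation and proximal collar stent stripping. Section 10.3.3 reports DOCE, each DOCE component, POCE and the proportion of study devices that malfunctioned.

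**The concern.** The study is meant to describe the safety of the device rather than of PCI in general, and section 3.4 says it is the device's first clinical use. There is no concurrent control arm to show what the same procedures would produce without it. Within the study, the means of separating device effects from procedural ones is therefore the causality grading that section 12.3 already asks for.

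The table list in section 10.3.2 makes no use of that separation. If it is followed as written, the final report need not state how many participants had a device-related event, or a serious one, outside the outcomes covered by MACE and DOCE. Section 11.2 says of its risk list: "The following adverse events are anticipated adverse events associated with all interventional procedures". Several entries, such as arterial perforation, could arise from the device or from the rest of the procedure, so the event name alone does not reveal the cause.

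**Working it through.** **Step 1: the plan's own figures.** These do not bear on table layout, but they fix what a change would leave alone. The inputs are in section 10.1: n = 85, success if at most 3 participants have MACE, performance goal 10%, assumed true rate 2%.

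- Alpha = P(X ≤ 3) with X ~ Binomial(85, 0.10) = 0.02451 (stated 0.0245).
- Power = P(X ≤ 3) with X ~ Binomial(85, 0.02) = 0.9088 (stated 0.91).
- Wilson 95% interval for 3/85, from [p + z²/2n ± z√(p(1−p)/n + z²/4n²)] / (1 + z²/n) with p = 0.0353 and z = 1.96: 1.2% to 9.9% (as stated in section 10.3.2).
- Enrolment = 85/(1 − 0.10) = 94.4, rounded up to 95 (as stated).

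All are reproduced, and none depends on how adverse events are tabulated.

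**Step 2: the four tables against the attribution provided for.**

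- Table (a): adverse device effects are counted among all events and not shown separately.
- Table (b): procedure and device relatedness are named as one category.
- Table (c): serious events, with no split by cause.
- Table (d): events requiring device discontinuation. This concerns what happened to the device's use, not what caused the event.

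None yields a count of adverse device effects or of serious adverse device effects.

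**Step 3: where device harm is visible anyway.**

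- Device-caused dissection, stent deformation and stent stripping: through MACE in the Safety Population (any participant into whom the device is introduced, section 10.2.1) and through the DOCE components.
- Malfunctions: as a proportion of devices under section 10.3.3. This counts devices, not participants harmed.
- DOCE uses the Performance Population (section 10.2.2), which also requires that the device was used as intended. Participants in whom it was introduced but not so used are in the Safety Population and not in DOCE.

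**Step 4: what is left.** Arterial perforation, branch occlusion, thrombosis and air embolus are listed in section 11.2 but are not named components of MACE or DOCE. Unless such an event counts as MACE, it appears in the section 10.3.2 tables, by event name and highest severity. A perforation row in table (b) would not say whether the event was graded to the device, the procedure or both.

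**Step 5: what counts as related.** Section 8.3 gives a threshold for POCE only (causal or probable). No threshold is given for table (b), so an event graded possible could be placed in it or left out.

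**The case against.** The strongest case against is that device safety is already reported where it matters most. The harms the protocol singles out are MACE components, every MACE is described, and section 10.3.3 adds DOCE, its components, POCE and malfunctions. The Medical Monitor reviews all adverse events (section 13.7). The slash in table (b) might mean that both relationships will be shown. And because both gradings are to be recorded for each event, the split could be made at reporting without loss.

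Much of this stands, and it limits the point to events outside those components. It does not remove it. DOCE covers a narrower population. The Medical Monitor's review is oversight during the study, not a reported result. The text does not say that the slash means a split; if it does, one sentence would settle the matter. That the split could be made later is a reason to specify it now, before the data are seen.

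A reader might go further and infer that a device signal would be buried among routine PCI complications. The documents do not support that. The tables run by event type, so bruising and perforation would sit on separate rows, and the plan specifies no pooled any-event count in which one could swamp the other. Attribution can be lost only within an event type. Section 11.2 lists possible events without frequencies, so nothing shows that procedural events would dominate.

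**Conclusion.** The point holds as a limited reporting gap. No planned table shows adverse device effects or serious adverse device effects alone, and for non-MACE events outside the DOCE components the planned output would not show whether the device or the procedure was held responsible.

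Its size cannot be given as a number: the documents contain no adverse-event rates, and the plan sets no test on these tables. The primary endpoint, the limit of 3 MACE in 85, alpha and power are unaffected. The conclusion assumes that table (b) is one combined category, which is the plain reading of the text, and that both causality gradings are recorded as section 12.3 directs.

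**What to change.** In section 10.3.2, with counts and percentages of participants over the Safety Population:

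1. Replace table (b) with (b1) device-related events (adverse device effects) and (b2) procedure-related events. Give each by event type with an any-event total, show events graded to both in both tables, and label the tables as non-MACE.
2. Add a table of serious adverse device effects, flagging any that are unanticipated as defined in section 12.1. State that it includes device-caused MACE meeting the serious definition. The present tables are confined to non-MACE events, so without that statement the table would omit such events and undercount.
3. State which of the five section 12.3 grades count as related for these tables, and whether the threshold is the same as for POCE.

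The cost is a few sentences of SAP text and two more tables (4 − 1 + 2 + 1 = 6). No new data are needed, and n, alpha and power do not change.
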